8.1.7 Patient's Global Assessment of Disease Activity

Subjects will complete the PGADA using a NRS. The range covers 0 (not active) to 10 (very active).

8.1.8 Total and Nocturnal Spinal Pain

The pain experienced by AS subjects is measured by 2 separate questions: 1) total pain in the spine due to AS (i.e. "How much pain of your spine due to spondylitis do you have?"); and 2) pain in the spine at night due to AS (i.e. "How much pain of your spine due to spondylitis do you have at night?") (Sieper et al, 2009; van der Heijde et al, 2005; Committee for Proprietary Medicinal Product/EWP/556/95, 2002).

The arithmetic mean of both questions describes the TNSP. If the response to one question is missing the TNSP will be taken as the response to the non-missing question. If both responses are missing, the TNSP will be regarded as missing.

8.1.9 Short Form – 36 Items Health Survey

The SF-36 (Version 2, standard recall) is a 36-item generic health-related quality of life (HRQoL) instrument that uses a recall period of 4 weeks. Items are grouped into 8 health domains as follows: Physical Functioning (10 items), Role Physical (4 items), Bodily Pain (2 items), General Health (5 items), Vitality (4 items), Social Functioning (2 items), Role Emotional (3 items), Mental Health (5 items). The concepts represented by these scales contribute to physical, mental, and social aspects of HRQoL. One additional item (Question 2) asks respondents about perceived stability or change in health (Health Transition) over the past year. The classification of the questionnaire items to the health scales is shown in [Section 12.2](#).

In addition to the domain scores, the Physical Component Score (PCS) and Mental Component Score (MCS) are calculated from the 8 domains (excluding the Health Transition item).

Component scores appreciate the impact of each domain on physical and mental health status.

The 2 SF-36 component summaries (PCS and MCS) and the 8 domain scores are standardized with a mean of 50 and a SD of 10 in the general US population. An individual respondent's score that falls outside the T-score range of 45 to 55 should be considered outside the average range for the general US population. When considering group-level data, a score below 47 should be considered indicative of impaired functioning within that health domain or dimension. Similar to individual respondent data, group mean scores 47 or greater should be considered average or above average as compared to the general US population. Higher scores indicate a better health status.

For the calculation of the SF-36 domain scores and the component summaries PCS and MCS, the scoring software Quality Metric's PRO CoRE will be used). The software uses updated 2009 US population norms and applies a Full Missing Score Estimation method as follows:

- A health domain score (except the Physical Functioning domain) will be estimated provided that at least 1 non-missing response is available within that domain.
- For the Physical Functioning domain item response theory will be used to develop a model for estimates of the missing score.

- Regression methods are then applied to estimate the PCS and the MCS on the basis of the scores for each domain.

8.1.10 Ankylosing Spondylitis Quality of Life

The ASQoL consists of 18 items, each with a score of 0 = no or 1 = yes, so that the sum score ranges from 0 to 18, with higher scores indicating worse quality of life.

If 3 or fewer items are missing, the missing responses will be imputed with the mean of the available responses from that visit to calculate a total score. If more than 3 items are missing, the total score will be left missing.

Note that in the raw data the results are coded as 1 = yes and 2 = no; these will be re-coded as above prior to calculation of the ASQoL score.

8.1.11 Hospital Anxiety and Depression Scale

The HADS was chosen for its well-established psychometric properties and its use in clinical research on biological therapy in subjects with chronic plaque psoriasis (Langley et al, 2010; Dauden et al, 2009). The HADS consists of 14 items, each scored from 0 to 3.

HADS-A will be calculated as the sum of the scores for items 1, 3, 5, 7, 9, 11, 13, and HADS-D will be calculated as the sum of the scores for items 2, 4, 6, 8, 10, 12, 14. Each score ranges from 0 to 21 with higher scores indicating a worse state. A score below 8 is considered normal and a score of 15 and above is considered severe (Snaith and Zigmond, 1994). If any of the 7 items required to calculate the HADS-A or HADS-D are missing then the HADS-A or HADS-D will be treated as missing.

A flag to identify “normal” depression and anxiety status at each visit (defined as having HADS-D and HADS-A <8 at the same visit) will be derived.

8.1.12 High-sensitivity C-reactive protein levels

Note that high sensitivity C-reactive protein will be referred to as CRP throughout this SAP. CRP levels will be analyzed by the central laboratory. Any CRP assessments performed at local laboratories will not be considered for efficacy analyses (including ASDAS-CRP).

Due to a change in laboratory vendor between AS0008 and AS0009, CRP values from the AS0009 laboratory have been calibrated to match those from the AS0008 laboratory, and these values will be used for all CRP summaries and listings.

In AS0008 the LLOQ was 0.16mg/L, however in AS0009 it was possible to measure concentrations below this value and report these as a numeric result. The LLOQ in AS0008 will therefore be applied to the AS0009 data in order to retain consistency in reporting across the studies. Thus, numeric values of less than 0.16mg/L (<0.16mg/L) in AS0009 will be imputed with half the LLOQ from AS0008 (ie, 0.08mg/L) prior to summary reporting or any derivation of composite parameters (NB different criteria apply for the derivation of ASDAS-CRP as described in [Section 8.1.2](#)). The original values will be included in the listing.

CRP values at AS0008 Baseline and AS0009 EV will be taken from the AS0008 database (Baseline and Week 48 records respectively).

Any CRP values $\geq 500\text{mg/L}$ will be set to missing prior to performing the MI procedure ([Table 4-1](#)) as these are considered to be extreme outliers.

8.2 Statistical analyses of secondary efficacy variables

The following secondary efficacy variables will be summarized for the FAS by treatment group at the completion of AS0008 and overall:

- ASAS40 response relative to AS0008 Baseline at AS0009 Week 48
- ASAS20 response relative to AS0008 Baseline at AS0009 Week 48
- Change from AS0008 Baseline in BASDAI at AS0009 Week 48

One set of summaries will be produced using data following NRI (ASAS responses) or MI (BASDAI) and another set using OC data. For ASAS responses, a further set of tables will be produced after the response variables have been derived following MI of the individual components. Summaries will not be presented for individual components of the ASAS (with the exception of PGADA which is a standalone endpoint).

8.3 Statistical analyses of other efficacy variables

The following other efficacy variables will be summarized for the FAS at scheduled visits in accordance with the schedule of study assessments in [Table 2-1](#), by treatment group at completion of AS0008 and overall:

- ASAS40, ASAS20 and ASAS5/6 response at each visit in AS0009, relative to AS0008 Baseline.
 - Summaries will not be presented for individual components of the ASAS with the exception of PGADA which is a standalone endpoint.
- ASAS-PR response at each visit in AS0009, relative to AS0008 Baseline.
- Change from AS0008 Baseline in ASDAS-CRP at each visit in AS0009.
 - Summaries will not be presented for the individual components of the ASDAS-CRP with the exception of PGADA which is a standalone endpoint.
- ASDAS-ID at each visit in AS0009 (including Low Disease Activity, High Disease Activity and Very High Disease Activity categories).
- Change from AS0008 Baseline in BASDAI at each visit in AS0009.
- Change from AS0008 Baseline in BASFI at each visit in AS0009.
- Change from AS0008 Baseline in BASMI at each visit in AS0009.
- Change from AS0008 Baseline in MASES at each visit in AS0009.
 - Only subjects with MASES >0 at AS0008 Baseline will be included.
- Change from AS0008 Baseline in PGADA at each visit in AS0009.
- Change from AS0008 Baseline in TNSP at each visit in AS0009.
- Change from AS0008 Baseline in SF-36 PCS and MCS at each visit in AS0009.

- Change from AS0008 Baseline in SF-36 domain scores (Physical Functioning, Role Physical, General Health, Bodily Pain, Vitality, Social Functioning, Role Emotional and Mental Health) at each visit in AS0009.
- Change from AS0008 Baseline in ASQoL at each visit in AS0009.
- Change from AS0008 Baseline in HADS-A and HADS-D scores at each visit in AS0009.
- Incidence of depression and anxiety status “normal” as defined by HADS-A and HADS-D scores below 8 at each visit in AS0009
- Change from AS0008 Baseline (expressed as ratio to Baseline) in CRP at each visit in AS0009
 - For CRP the rules for handling values that are lower than the LLOQ identified in AS0008 will be followed as per [Section 8.1.12](#).

One set of summaries will be produced for all the above parameters using data following NRI or MI as appropriate, as described in Section [4.2.1](#).

For ASAS40, ASAS20, ASAS5/6 and BASDAI, an additional set of summaries will be produced using OC data.

Finally, for ASAS40 and ASAS20 responses only, a further set of tables will be produced after the response variables have been derived following MI of components.

The summary tables for CRP will display the absolute value and ratio to AS0008 Baseline and will contain n, geometric mean (and 95% CI), median, first and third quartile (Q1 and Q3), minimum. Any values for the ratio to AS0008 Baseline below 0.01 will be presented as <0.01 in the listing and summary table.

8.3.1 Maintenance of response

ASAS20, ASAS40 and ASAS5/6 response relative to AS0008 Baseline will, in addition, be summarized at each post-Baseline visit in AS0008 through to AS0009 Week 208 (or to AS0009 Week 204 for ASAS5/6 response), by treatment sequence as defined in [Section 3.7](#). These summaries will be restricted to subjects with a response at AS0008 Week 12, and data will be reported following NRI. Summaries will be based on the FAS for AS0009.

8.4 Subgroup analysis

Subgroup summaries will be performed on the following efficacy variables for the FAS:

- ASAS20 response at AS0009 Week 48, relative to AS0008 Baseline.
- ASAS40 response at AS0009 Week 48, relative to AS0008 Baseline.
- ASAS5/6 response at AS0009 Week 48, relative to AS0008 Baseline.
- BASDAI change from AS0008 Baseline at AS0009 Week 48.

Subgroups are defined in [Section 4.8](#).

All subgroup analyses are based on imputed data using either NRI (ASAS endpoints) or MI (BASDAI).

8.5 Impact of COVID-19

Additional sensitivity analyses as a result of the global COVID-19 pandemic are not anticipated as the onset of the pandemic was subsequent to all subjects completing Week 48 and therefore there is no impact on the analysis of the secondary efficacy endpoint.

9 PHARMACOKINETICS AND PHARMACODYNAMICS

9.1 Pharmacokinetics

Bimekizumab plasma concentrations will be summarized at each scheduled visit in AS0009 by treatment at completion of AS0008 and overall, using the SS.

If bimekizumab plasma concentration measurements are deemed to be BLQ, then for calculation of the derived statistics this sample result will be set to half the LLOQ. Descriptive statistics will be calculated only if at least 2/3 of the values are above the LLOQ at a given visit and $n \geq 3$. If this is not the case, only median, minimum, and maximum will be presented.

In addition, geometric mean bimekizumab plasma concentration (with 95% CI) time curves will be plotted versus time on linear and semi-logarithmic scales by treatment group at completion of AS0008.

The summary table for bimekizumab plasma concentrations will display n, geometric mean (and 95% CI), geometric CV%, arithmetic mean, SD, median, minimum, and maximum, where the geometric CV% is calculated using the following formula:

$$CV\% = \sqrt{e^{SD_{ln}^2} - 1} \times 100 \quad (13)$$

here SD_{ln} represents the standard deviation of the ln-transformed plasma concentration values.

Geometric mean plots will be repeated by cumulative ADAb positivity and treatment:

- The ADAb positive status will be considered in a cumulative manner at each time point:
 - A subject will be counted positive from the first time point at which the subject had a positive ADAb sample result regardless of any subsequent missing or negative ADAb sample results.
 - If a subject has only negative ADAb samples or only one missing sample with all negative ADAb samples up to a specific time point, the subject will be classified as negative at that time point. If the AS0008 Baseline sample is missing, then the sample will be classified as being negative for the cumulative ADAb status.
 - Thus, the number of subjects included in the geometric mean for positive and negative categories will vary by time point for each treatment.
- Two plots will be presented each displaying bimekizumab plasma concentration data in AS0009 only:
 - Considering cumulative ADAb in status in AS0009 only at each time point in AS0009
 - Considering cumulative ADAb status in AS0008 and AS0009 at each time point in AS0009

- Each plot (linear and semi-logarithmic) will be presented by treatment group at completion of AS0008 and ADA_b positive status (4 lines per plot)

The following rules will be implemented for PK concentration summaries and corresponding figures:

- If the dosing for a visit is performed more than 14 days prior to, or more than 14 days after the scheduled dosing interval (28 days), then the plasma concentration obtained at that dosing visit will be excluded from the PK summaries and figures. Thus, if the dosing interval is less than 14 days or greater than 42 days, this rule will apply. This will also apply to doses administered at an unscheduled visit.
- If a PK sample is collected >14 days after the preceding dose and up to 1 hour after the dose at the current visit, the PK concentration for that sample will be associated with the scheduled visit and summarized accordingly. This will include unscheduled assessments as described in [Section 3.5](#) (if a dose was administered at an unscheduled visit). Samples collected outside this window will be excluded from the PK summaries and figures and will be listed only.
- Individual samples collected at a scheduled visit at which dosing was not performed (eg, due to AE) will be retained in the PK summaries and figures for the specific visit if these are collected >14 days and <42 days after the preceding dose, as these reflect the trough concentration from the preceding dose. The sample obtained at the subsequent scheduled visit will be excluded from the summaries (regardless of dosing) as this will not reflect a steady-state trough concentration (as the previous dose was not administered). Thereafter PK samples will be included in the summaries assuming dosing has resumed and the sample was obtained within the required window of >14 days after the preceding dose and up to 1 hour after the dose at the current visit.
 - Note samples collected at Week 208 or at the ET visit will be retained in the PK summaries and figures if they are collected >14 days and <42 days after the last dose received

These rules will not apply for the SFU visit as no dosing is planned at this visit. All concentrations obtained at the SFU visit will be included in the summary tables (but will not be included in the figures).

Bimekizumab plasma concentrations will be listed for the SS, separately for AS0009 and for data from AS0008 and AS0009 combined. All concentrations will be listed as received, prior to substitution of any BLQ values. The listing of the AS0009 data will include flags for concentrations that were excluded from the summary statistics where the reason for exclusion will be one of the following:

- Dosing performed out of window
- Sample collected out of window relative to current dose
- Sample collected out of window relative to previous dose
- Missed dose at preceding visit

- More than one sample obtained at the same visit

All plasma concentration data will be reported in ug/mL in the tables, figures and listings.

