7.7 Procedures for monitoring subject compliance

During the Treatment Period of this study, IMP will be administered in the clinic during the first 3 months of treatment (Visit 1 [Entry Visit] through Visit 4 [W12]) and compliance will be determined at the visit by study personnel. Thereafter, self-administration at home will be possible at the following weeks: Weeks 16, 20, 28, 32, 40, 44, 52, 56, 64, 68, 76, 80, 88, 92, 100, 104, 112, 116, 124, 128, 136, 140, 148, 152, 160, 164, 172, 176, 184, 188, 196, and 200. Dates and time of self-administration will be captured using a subject diary. All used PFS will be disposed of by subjects/caregivers/appropriate designee as determined by the Investigator in an acceptable disposal (sharps) container directly after the administration.

Drug accountability must be recorded on the Drug Accountability Form. If a subject is noncompliant with the study procedures or medications that may present a risk to the safety of the subject in the opinion of the Investigator, then the subject should be withdrawn as described in [Section 6.3](#).

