2.2.3 Pharmacokinetic/pharmacodynamic variables

2.2.3.1 Other pharmacokinetic variable

The pharmacokinetic variable is the plasma concentration of bimekizumab at each visit (AS0009 EV, Week 12, 24, 36, 48, 72, 96, 120, 144, 168, 192, 208, SFU).

No pharmacodynamic variables are defined.

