10.1 Extent of exposure

Study medication duration will be calculated for each of the following using the imputation rules in [Section 4.2.4](#) for partial treatment end dates:

- Total bimekizumab duration: Between the first dose of bimekizumab in AS0008 and last dose of bimekizumab in AS0009.
- Total duration on bimekizumab 160mg: Between the first and last dose of bimekizumab 160mg (in AS0008 or AS0009).

- Duration on bimekizumab 320mg: Between the first dose of bimekizumab 320mg in AS0008 and first dose of bimekizumab 160mg in AS0009 (calculated only for subjects who took bimekizumab 320mg in AS0008).
- Duration on bimekizumab 160mg in AS0009: Between the first and last dose of bimekizumab 160mg in AS0009.

The duration of exposure will be calculated as outlined in [Table 10–1](#).

Table 10–1: Study medication duration

Duration Category	Start date	End date	Study medication duration
Total BKZ duration	First dose of BKZ in AS0008	Last dose of BKZ in AS0009	End date – start date + 28 ^a
Total duration on BKZ 160mg	First dose of BKZ 160mg in AS0008 or AS0009	Last dose of BKZ 160mg in AS0009	End date – start date + 28 ^a
Duration on BKZ 320mg	First dose of BKZ 320mg in AS0008	First dose of BKZ 160mg in AS0009	End date – start date + 1
Duration on BKZ 160mg in AS0009	First dose of BKZ 160mg in AS0009	Last dose of BKZ 160mg in AS0009	End date – start date + 28 ^a
Subjects who died ^b	Start date for each option as above	Date of death	End date – start date + 1

BKZ=bimekizumab.

^a 28 days refer to one half-life of BKZ.

^b For subjects who died, the date of death will be used to replace the end date in the calculation of study medication duration only if the subject died within the dosing interval (i.e., within 28 days following the last dose [not applicable for duration on BKZ 320mg]) or if the subject died before dosing in AS0009 (for duration on BKZ 320mg). If the subject died more than 28 days after the last dose of BKZ in AS0009 the study medication duration will be calculated using the dosing interval of 28 days.

The exposure time at risk will be calculated as outlined in [Table 10–2](#).

Table 10–2: Exposure time at risk

Exposure Category	Start date	End date	Duration of Exposure
Total BKZ exposure	First dose of BKZ in AS0008	Last dose of BKZ in AS0009	Minimum of [(End date – start date + 140 ^a) +1] and (Date of last clinical contact ^b – start date + 1)

Table 10–2: Exposure time at risk

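### SAP 9.1 drops the next PK sample after a missed visit dose for a reason that is untrue once dosing has resumed, yet keeps some troughs that are further below steady state

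*SAP*

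**What the plan says.** SAP section 9.1 gives three rules for including a concentration in the PK summaries and figures.

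- **Interval rule.** A concentration is excluded when the dose at that visit was given too early or too late relative to the 28-day schedule: "if the dosing interval is less than 14 days or greater than 42 days, this rule will apply".
- **Sample window.** The sample must be more than 14 days after the preceding dose and no later than 1 hour after the current one.
- **Missed-dose rule.** A sample from a scheduled visit without dosing is kept if it falls more than 14 and less than 42 days after the preceding dose. For the sample after that: "The sample obtained at the subsequent scheduled visit will be excluded from the summaries (regardless of dosing". The reason given is that "this will not reflect a steady-state trough concentration (as the previous dose was not administered".

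A note under the third rule keeps Week 208 and early-termination samples that fall more than 14 and less than 42 days after the last dose. The listing reason for a missed dose refers to the preceding visit, not the preceding dose.

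SAP section 2.2.3.1 places PK samples at the entry visit and "Week 12, 24, 36, 48, 72, 96, 120, 144, 168, 192, 208, SFU". Dosing is every 4 weeks. Protocol section 7.7 allows home dosing from Week 16 in the weeks between the 12-weekly site visits ("Thereafter, self-administration at home will be possible at the following weeks").

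**The concern.** The stated reason holds only if one dose separates consecutive PK samples. Here several do. A subject who misses the dose at a PK visit and then resumes has received the dose before the next sample, so the sample is dropped for something that did not happen.

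The rule also looks only at doses missed at a visit where a sample was drawn. A home dose missed later, and so closer to the next sample, does not trigger it because no sample is taken at home. Only the interval rule can catch such a dose, and it looks only at the last interval.

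At stake are the by-visit concentration summaries and the geometric mean plots, including those split by anti-bimekizumab antibody status. Missed doses are foreseeable: SAP section 12.5 provides categories for missed and temporarily stopped dosing during the pandemic. SAP section 8.5 says the pandemic began after all subjects had completed Week 48, when most PK gaps are 24 weeks.

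**Working it through.** **Inputs.** Dosing interval 28 days and limits of 14 and 42 days (SAP 9.1); PK weeks (SAP 2.2.3.1); 52 expected doses (SAP 7); 32 home-dosing weeks (Protocol 7.7); half-life from SAP Table 10-1, footnote a: "28 days refer to one half-life of BKZ"; permitted spacing between doses of 21 to 35 days (SAP Table 2-1, footnote a). The linear one-compartment model is my assumption, as is the half-life range of 21 to 35 days used for sensitivity.

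**The plan's own figures.** 28 − 14 = 14 and 28 + 14 = 42, which matches the SAP. 204/4 + 1 = 52 doses, which also matches.

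**Doses between PK samples.** 12-week gap: 12/4 − 1 = 2. 24-week gap: 24/4 − 1 = 5. 16-week gap (Week 192 to 208): 16/4 − 1 = 3.

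**Effect of one missed dose.** Let r = 0.5^(28/half-life). The steady-state trough is proportional to r + r² + … = r/(1 − r). A dose missed k intervals before the sample removes r^k, a fraction r^(k−1)(1 − r) of the trough. At a 28-day half-life, r = 0.5 and the loss is 0.5^k.

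| Weeks since missed dose | k | Trough, % of steady state (28-day half-life) | Range, half-life 21–35 days |
|---|---|---|---|
| 4 | 1 | 50.0 | 39.7–57.4 |
| 8 | 2 | 75.0 | 75.0–76.1 |
| 12 | 3 | 87.5 | 86.0–90.5 |
| 16 | 4 | 93.8 | 91.9–96.2 |
| 20 | 5 | 96.9 | 95.4–98.5 |
| 24 | 6 | 98.4 | 97.3–99.4 |

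**Applying the rules to one missed dose, all others given on schedule.**

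- Week 12 (PK visit) missed: Week 24 sample at 87.5%, last interval 28 days. Excluded by the missed-dose rule.
- Week 48 (PK visit) missed: Week 72 sample at 98.4%, after five doses (Weeks 52 to 68). Excluded if the rule means the next PK visit.
- Week 16 (home) missed, Week 20 given: Week 24 sample at 75.0%, last interval 28 days. Kept.
- Week 64 (home) missed, Week 68 given: Week 72 sample at 75.0%. Kept.
- Week 20 (home) missed: Week 24 sample at 50.0%, interval 56 days. Excluded by the interval rule. With permitted spacing the interval is 2 × 21 = 42 to 2 × 35 = 70 days, so only an interval of exactly 42 days escapes.
- Week 60 (site visit, no PK sample) missed: Week 72 sample at 87.5%. Kept on the next-PK-visit reading, although the same loss at Week 24 is excluded.
- Week 192 (PK visit) missed: Week 208 sample at 93.8%. Excluded by the missed-dose rule on the next-PK-visit reading, but kept by the Week 208 note.

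**The case against.** Four points can be made for the SAP.

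1. *The phrase may not mean the next PK visit.* The next site visit after Week 48 is Week 60, which has no PK sample; on that reading nothing is excluded at Week 72 and the 1.6% figure falls away. This stands, so the 24-week example is conditional. It does not rescue the rule: every site visit from Week 12 to Week 48 is a PK visit, so the Week 24 exclusion holds on either reading. If the next dosing visit is meant, no sample exists there and the exclusion is empty.

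2. *A trough 12.5% low is not strictly at steady state.* True. Calling every excluded sample near steady state would overstate the case; that description fits the 24-week gap only. The stated reason is still false, because the dose before the sample was given.

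3. *A 25% shortfall lies within what the SAP already tolerates.* At a 42-day interval the trough is 0.5^(14/28) = 71% of its 28-day value, about 29% low, and it is kept. This stands. Keeping the 75% trough is therefore not an error in itself, and whether to look back one dose or two is a choice. What cannot be defended is keeping it while dropping one at 87.5%.

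4. *Nothing is lost.* All concentrations are listed and AS0009 exclusions are flagged. True, but the summaries and figures still follow the rule.

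**Conclusion.** The missed-dose rule is wrong as written. It excludes samples for a reason that the trial's own schedule makes untrue once dosing has resumed, and its ordering is inverted: troughs at about 87.5% of steady state (12-week gap), and about 98.4% (24-week gap, on the next-PK-visit reading), are excluded while troughs at about 75% are kept. The ordering holds for half-lives of 21 to 35 days. It rests on a linear one-compartment model, a single missed dose, and a subject otherwise at steady state on 160 mg; subjects who entered on 320 mg are not at that steady state in the first weeks.

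A reader might infer that any more recent missed home dose slips through. It does not: the dose immediately before the PK visit, which has the largest effect, is caught by the 42-day limit. The gap concerns home doses missed 8 weeks or more before the sample.

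A reader might also infer that the PK results will be materially biased. The documents do not support that. The percentages are per sample, missed-dose frequency is not given, and the effect on any geometric mean cannot be computed. The impact is confined to descriptive PK summaries and figures; no primary or secondary endpoint is affected.

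**What to change.** - Delete the visit-based exclusion. Decide inclusion from actual administration dates, site and home: exclude a sample only if the scheduled dose or doses immediately before it were missed, or if the dosing interval is outside 14 to 42 days.
- Prespecify the look-back. One dose keeps troughs at 75% or more and adds little to the present interval rule; two doses keeps those at 87.5% or more. Either removes the inversion.
- Apply the same rule at Week 208 and early termination, so that the missed-dose rule and its note agree.
- Reword the listing reason to refer to the preceding dose or doses.

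The cost is SAP wording and a small programming change. Administration dates are already collected for site and home doses. Some excluded samples would return to the summaries and, with a two-dose look-back, some included ones would move to the listing.
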